**Protocol ID: B10304016**

**Created Date: 6th August 2018**

**Participants:**

experimental group: 51 persons; control group: 51 persons

[figure not shown]
**Inclusion criteria:**

- a. Adults that age 20 above and 50 below
- b. Clinical diagnosis confirmed as allergic rhinitis
- c. Conscious, no mental or cognitive impairment
- d. Able to read, write or communicate in Mandarin, Taiwanese or Hakka, and agreed to participate

[figure not shown]
**Exclude criteria:**

- a. Inflammatory skin wounds on the back of the shoulder, neck or lower back
- b. Polyposis
- c. Acute and chronic sinusitis
- d. Vasomotor rhinitis

## Experiment procedure:

## Experimental scheme:

**Assessment Scale:**

1. Basic demography questionnaire
2. Taiwanese Version of the 22-Item Sino-nasal Outcome Test (SNOT-20)
3. WHOQOL-BREF questionnaire (Allergic rhinitis questionnaire scale based on Taiwan's concise version of the World Health Organization Quality of Life Questionnaire)
4. Oral medication: type / dose / frequency /statistic in between

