**Method of Statistic:**

1. SPSS 18.0
2. The subjects were randomly grouped into experimental group and control group.
3. re-test was carried out before the experiment, 1st post-test was carried out at the 4th week and 2nd post-test was carried out at the 12th week. The data of the Pre- and post-test at the 4th & 12th week for both groups were statistically analyzed.
4. Independent t -test or chi-square test was carried out before the test for participant's basic information in both groups to examine the difference between the two groups.
5. Descriptive statistical analysis.
6. The data of pre- and post-test for two groups were compared by single-factor or two-factor analysis of variance (ANOVA).

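### Does labelling the symptom scale as both 22-item and SNOT-20, and describing the WHOQOL-BREF in rhinitis terms, leave these outcomes unusable?

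*Protocol*

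**What the plan says.** The Assessment Scale section of the protocol lists four entries. Entry 2 is the symptom scale: "Taiwanese Version of the 22-Item Sino-nasal Outcome Test (SNOT-20". Entry 3 is the quality-of-life scale. It opens with "WHOQOL-BREF questionnaire" and continues in brackets with "Allergic rhinitis questionnaire scale based on" the short Taiwanese form of the WHO questionnaire.

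Neither scale is named again, and no item list or score range appears. The protocol does not rank its outcomes; the two questionnaires stand beside medication use and two blood measures (the latter under Examine).

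The Method of Statistic section sets the assessments at pre-test, week 4 and week 12 for both randomised groups. It states the analysis in general terms: "The data of pre- and post-test for two groups were compared by single-factor or two-factor analysis of variance (ANOVA".

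**The concern.** A total score depends on how many items are summed, so an instrument with two item counts looks like an outcome that has not been fixed. This is also the only sino-nasal symptom scale in a trial of allergic rhinitis. If the printed form, the scoring sheet and the report followed different versions, scores would not be on one scale, and a reader could not confirm that the reported outcome was the planned one.

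Entry 3 raises a related doubt. The leading name suggests a standard quality-of-life instrument, while the words "Allergic rhinitis questionnaire scale based on" could describe a disease-specific adaptation. On that reading, the trial's only symptom scale and its only quality-of-life scale are both uncertain.

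**Working it through.** There is no figure in the plan to reproduce, so the check is mainly a comparison of the text, with a little arithmetic on its possible size.

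**1. Entry 2.** The full name, "Taiwanese Version of the 22-Item Sino-nasal Outcome Test", gives 22 items. The acronym in "22-Item Sino-nasal Outcome Test (SNOT-20" gives 20. The difference is 22 − 20 = 2 items. The name and acronym contradict each other, and the visible text does not resolve it.

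**2. Entry 3.** It contains no conflicting numbers and no two incompatible names. The bracket may be a loose expansion of the acronym, with the disease mentioned because the participants have rhinitis, or it may describe an adapted form. The text supports either reading, so this is an ambiguity and not a contradiction.

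**3. Possible size for entry 2.** Let every item be scored from 0 to k and summed, with the same k for both forms. The protocol does not give k.
- Maximum totals are 22k and 20k, with ratio 22/20 = 1.10 for any k.
- The gap between the maxima is 22k − 20k = 2k. With k = 5 as an assumption, this is 110 − 100 = 10 points; with k = 4 it is 88 − 80 = 8.
- Reading 2k as the most by which one person's score could differ between forms needs a further assumption: that the 20 items all appear unchanged among the 22. The protocol does not say so. If the score is a mean per item, the two ranges are the same.

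**4. Does the maximum total matter to the test?** Not by itself. If all scores are multiplied by 1.10, every mean square is multiplied by 1.10² = 1.21, in both the numerator and the denominator of the F ratio, and the factor cancels. The two forms could differ in content and precision, but the length of the scale alone does not alter an ANOVA result.

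**5. What would damage the comparison?**
- *One form for everyone at every visit.* Both groups are measured alike, and the between-group comparison is sound whichever label is the slip.
- *A switch of form between visits, the same in both groups.* Change within a group would be distorted. Because allocation is random, the two groups would still be measured alike at each visit.
- *Different forms in the two groups.* This would bias the comparison.

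The protocol gives one entry for the scale and one schedule for both groups. Nothing in it points to the second or third case.

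**6. Does anything else in the protocol use the item count?** The sample size is stated as "experimental group: 51 persons; control group: 51 persons", with no score-based effect or standard deviation behind it. The ANOVA sentence names no instrument and no threshold on either scale. Replacing 20 by 22, or 22 by 20, leaves every other line as it is.

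**The case for a change.** The strongest case for a change is that the protocol, not the analysis plan, fixes which questionnaire participants complete, and here it does so with two incompatible identifiers. Correcting them would cost two lines of wording and a check of the printed forms. A reader who wants to compare the results with reference values from elsewhere needs to know the version.

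Much of this stands. The slip in entry 2 is certain, the document does not show which half is wrong, and a report that copied the line unchanged would mislabel its scale. Comparison with outside values would be unsafe until the version is known.

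The wider claims do not stand. Calling these the main outcomes goes beyond a protocol that ranks none. Calling them unidentified overstates it, since entry 2 clearly points to a Taiwanese version of the Sino-nasal Outcome Test and leaves only the item count in doubt. Loss of comparability across visits needs two forms in use, which the text does not suggest. A stated score range is scoring detail that an analysis plan commonly supplies, and the time points are already given. The headings for the procedure and scheme have no text beneath them in the copy at hand, so further detail on the instruments may simply not be shown.

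**Conclusion.** Entry 2 is a clerical slip, and entry 3 is a loosely worded description. Neither changes a stated number, an analysis or a conclusion of the trial, so no change to the plan follows.

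The size is 2 items, or 10% of the shorter form's maximum total under equal item ranges and summed scoring. Any figure in points rests on an item range, and for a single person also on nested items, that the protocol does not supply.

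The conclusion assumes that one form of each questionnaire was given to both groups at all visits, which is the natural reading of a single list with a single schedule. The analyst can see from the printed form whether it has 20 or 22 items, and whether the quality-of-life form is standard or adapted, and can name each accordingly in the report. Evidence that forms differed between the groups would overturn this view; the protocol contains none.

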**Examine:**

5. Ig-E blood examination (pre- and post-test)
6. Eosinophil cationic protein (pre- and post-test)

**Method of Statistic:**

1. SPSS 18.0
2. The subjects were randomly grouped into experimental group and control group.
3. re-test was carried out before the experiment, 1st post-test was carried out at the 4th week and 2nd post-test was carried out at the 12th week. The data of the Pre- and post-test at the 4th & 12th week for both groups were statistically analyzed.
4. Independent t -test or chi-square test was carried out before the test for participant's basic information in both groups to examine the difference between the two groups.
5. Descriptive statistical analysis.
6. The data of pre- and post-test for two groups were compared by single-factor or two-factor analysis of variance (ANOVA).

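### The arms are compared by one- or two-factor ANOVA that never uses the collected pre-test as a covariate, so precision is lost that ANCOVA would recover from the same data

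*Protocol*

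**What the plan says.** All references are to the Protocol.

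- **Method of Statistic, item 6** names the analysis: "The data of pre- and post-test for two groups were compared by single-factor or two-factor analysis of variance (ANOVA". It gives no covariate, and it does not say what the factors are or when each form applies.
- **Item 3** sets the measurement times. A measurement is taken at baseline ("re-test was carried out before the experiment"; the first letter of the word for pre-test is missing in the text), followed by two more: "1 st post-test was carried out at the 4 th week and 2 nd post-test was carried out at the 12 th week". The item says that the pre-test and post-test data of both groups are analysed.
- **Item 2** randomises subjects to the two groups.
- **Item 4**, the only other use of baseline data, tests "basic information in both groups to examine the difference between the two groups". It adjusts nothing.
- **Examine** marks both laboratory measures as taken before and after: "Ig-E blood examination (pre- and post-test" and "Eosinophil cationic protein (pre- and post-test".
- **Assessment Scale, item 4** lists "Oral medication: type / dose / frequency /statistic in between", with no pre-test stated.
- **Participants** gives the size: "experimental group: 51 persons; control group: 51 persons".

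**The concern.** The pre-test can enter the two named ANOVAs in two natural ways, and both give it the wrong weight. A single-factor ANOVA of a post-test gives it weight 0. The group-by-time term of a two-factor ANOVA is a contrast of changes and gives it weight 1. With equal variances the best weight is rho, the correlation between pre-test and post-test, and ANCOVA estimates that weight from the data.

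What is at stake is the width of the confidence interval and the power at 51 per arm, not validity. There is also a practical side. Item 6 allows either form, and on the same data the two estimates differ by exactly the observed pre-test difference between arms. A chance imbalance therefore pushes them in opposite directions.

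**Working it through.** **Inputs from the Protocol:** 51 per arm, randomised; pre-test, week 4 and week 12; one- or two-factor ANOVA.

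**Assumed, because the Protocol does not give them:** two-sided alpha 0.05, true effect 0.5 SD, equal SD at pre-test and post-test, rho 0.3/0.5/0.7. The Protocol states no power or effect size with its 51 per arm, so there is no planned figure to reproduce.

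**1. Variance of the arm difference** at one post-test, in units of 2·SD²/n. With n = 51 the unit standard error is sqrt(2/51) = 0.198 SD.

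| Analysis | Variance | rho 0.3 | rho 0.5 | rho 0.7 |
|---|---|---|---|---|
| Single-factor, post-test only | 1 | 1.00 | 1.00 | 1.00 |
| Two-factor, group-by-time | 2(1-rho) | 1.40 | 1.00 | 0.60 |
| ANCOVA | 1-rho² | 0.91 | 0.75 | 0.51 |

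The ratio of ANCOVA to post-only is 1-rho². The ratio to group-by-time is (1-rho²)/[2(1-rho)] = (1+rho)/2. Both are below 1 for rho strictly between 0 and 1. Simulation of 20,000 trials per rho gave variances for post-only, group-by-time and ANCOVA of 1.00/1.42/0.92 (rho 0.3), 1.03/1.02/0.78 (rho 0.5) and 1.00/0.60/0.52 (rho 0.7).

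**2. Power** from the noncentral t, with noncentrality 0.5/(0.198·sqrt(variance)), 100 df for the ANOVAs and 99 for ANCOVA.

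| Analysis | rho 0.3 | rho 0.5 | rho 0.7 |
|---|---|---|---|
| Post-only | 71% | 71% | 71% |
| Group-by-time | 56% | 71% | 90% |
| ANCOVA | 75% | 82% | 94% |

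At rho 0.5, an effect of 0.4 SD gives 52% for either ANOVA and 64% for ANCOVA. An effect of 0.6 SD gives 85% and 93%.

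**3. All three visits.** Assume compound symmetry and the same 0.5 SD effect at weeks 4 and 12. The squared deviations of the effects (0, 0.5, 0.5) from their mean sum to 1/6. The noncentrality is 25.5·(1/6)/(1-rho) = 4.25/(1-rho) on F(2, 200), and power is 58%/74%/93%.

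**4. Equivalent sample size.** Against post-only, 51/(1-rho²) = 56/68/100 per arm. Against group-by-time, 51·2/(1+rho) = 78/68/60 per arm.

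**5. Chance imbalance.** A pre-test difference of 0.2 SD is 0.2/0.198 = 1.01 standard errors, so one at least that large, in either direction, arises in about 31% of randomisations. Given a difference of 0.2 SD, the post-only contrast shifts by 0.2·rho = +0.06/+0.10/+0.14 SD. The group-by-time contrast shifts by -0.2·(1-rho) = -0.14/-0.10/-0.06 SD. ANCOVA removes the shift in expectation.

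**The case against.** The strongest reply is that nothing here is invalid. Both ANOVAs are unbiased under randomisation, and item 6 is a one-sentence outline whose detail an unseen SAP may complete. The first part stands, and the point is graded accordingly. The second does not carry: item 6 names the method, so a SAP using ANCOVA would depart from it.

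Other points:

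- **The two readings are not exhaustive.** This is true. A change score by arm is the group-by-time contrast already covered. The group main effect averaged over pre-test and one post-test is worse, with scaled variance 2(1+rho), or 3.0 at rho 0.5. A time effect within each arm does not compare the arms.
- **The inequality is a large-sample one.** Estimating the slope with 102 subjects multiplies the ANCOVA variance by 1+1/98. Power then becomes 74%/82%/94%. The order reverses only for rho below about 0.10 or above about 0.98, and the loss there is about 1% of variance at most.
- **The 2-df test is a weak comparator.** This is fair. A 1-df contrast of the mean post-test minus the pre-test has variance (1+rho)/2 + 1 - 2·rho = 1.05/0.75/0.45, and power of about 69%/82%/96%. That matches single-visit ANCOVA at rho 0.5 and beats it at 0.7. The like-for-like comparator is ANCOVA on the mean of the two post-tests. Its variance is (1+rho)/2 - rho² = 0.56/0.50/0.36, and its power, with the slope charged, is about 91%/94%/99%.
- **The imbalance argument counts the loss twice.** It is indeed the same loss seen within a single trial and should not be added to the power figures.

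**Conclusion.** The concern holds as a matter of efficiency. The Protocol commits the arm comparison to ANOVA forms that are less precise than ANCOVA at any ordinary positive correlation. For a 0.5 SD effect at one post-test, the cost lies between about 4 and 19 percentage points of power against group-by-time (94% v 90% at rho 0.7; 75% v 56% at rho 0.3). Against post-only it lies between about 4 and 23 points (75% v 71%; 94% v 71%). The gain is small against post-only when rho is low and against group-by-time when rho is high. Because rho is unknown in advance, ANCOVA is the safe choice.

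Only the 51 per arm, the randomisation and the visits come from the Protocol. The effect size, alpha, equal variances, compound symmetry and rho are assumptions, and the result is a range. The change is advisable, but the trial's validity does not depend on it.

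**What to change.** Reword item 6 of Method of Statistic. Compare the arms at weeks 4 and 12 by ANCOVA, or by an equivalent repeated-measures model of the two post-tests, with the same outcome's pre-test value as covariate. Make the adjustment whatever imbalance is observed. Apply it to SNOT, WHOQOL-BREF, IgE and eosinophil cationic protein, the last two at whichever post-test is taken. Oral medication has no stated pre-test and stays outside the change. Item 4 need not change for this purpose, but its tests should not decide whether to adjust.

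The cost is the wording of one item and one degree of freedom per model, with no new data. The item is written in the past tense. If outcome data have already been analysed, report the ANCOVA beside the ANOVA and label it as a later change.

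### Item 6 leaves open which ANOVA compares the arms over three visits, and each candidate handles participants who leave after week 4 badly; a likelihood-based mixed model should be named instead

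*Protocol*

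**What the plan says.** The protocol plans two randomised arms (Participants: "experimental group: 51 persons; control group: 51 persons"; Method of Statistic, item 2: "The subjects were randomly grouped into experimental group and control group"). Item 3 places a test before the experiment and post-tests at weeks 4 and 12, and adds: "The data of the Pre- and post-test at the 4 th & 12 th week for both groups were statistically analyzed". Item 6 gives the comparison: "The data of pre- and post-test for two groups were compared by single-factor or two-factor analysis of variance (ANOVA". Item 1 names SPSS 18.0 as the software.

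Item 6 does not name the factors. It does not say whether the ANOVA is for repeated measures, whether all three visits enter one model, or whether an incomplete participant is kept. The protocol gives no expected withdrawal rate.

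**The concern.** With two arms and three visits, group by time is the natural reading of a two-factor ANOVA, and its usual repeated-measures form uses one row per participant. A person who attends the pre-test and week 4 and then leaves has an incomplete row and is dropped, so a week-4 result that was collected is thrown away. The other two readings have faults of their own:

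- **Single-factor ANOVA at each visit.** Week 4 is intact. At week 12 only those who stayed are compared, and the week-4 results of those who left, which may explain why they left, are ignored.
- **Factorial group-by-time ANOVA on stacked rows.** All observed rows are kept, but three measurements on one person are treated as if they came from three people. The week-12 cell still holds only those who stayed.

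At stake is whether the randomised comparison of 51 with 51 becomes a comparison of completers. In the repeated-measures form, that would extend to a week-4 result for which nothing need be missing.

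**Working it through.** **Inputs.** From the protocol: 51 per arm; visits at pre-test, week 4 and week 12; ANOVA. Assumed, because the protocol gives none: SD 1 at each visit, equal correlation between visits (0.5 or 0.6), loss after week 4 of 10–30%, true effect 0 or −0.5 SD (lower is better). The protocol has no figure on this point to reproduce.

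**1. What each form keeps.** In one simulated trial of 102 participants with random loss after week 4, 75 had all three visits and 27 lacked week 12.

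- Repeated measures, one row per person: 75 kept, although 102 had a week-4 value.
- Single-factor at week 4: 102 kept.
- Factorial on stacked rows: 75 × 3 + 27 × 2 = 279 rows, all kept.

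**2. Loss unrelated to response.** There is no bias, only lost precision. The standard error (SE) of an arm difference with 51 per arm is √(2/51) = 0.198 SD. With 10% loss (45.9 per arm) it is √(2/45.9) = 0.209; with 20% (40.8 per arm), √(2/40.8) = 0.221. In the repeated-measures form this cost falls on week 4 as well.

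**3. Loss that depends on response.** Large simulation (400,000 per arm), correlation 0.5, outcome = change from pre-test, withdrawal logistic in the week-4 change. Entries are completers-only arm differences (experimental minus control, SD) at 10 / 20 / 30% control-arm loss.

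| Withdrawal depends on response in | True effect | Week 4 | Week 12 |
|---|---|---|---|
| neither arm | 0 | no bias | no bias |
| both arms, same rule | 0 | no bias | no bias |
| both arms, same rule | −0.5 | −0.467 / −0.456 / −0.435 | −0.488 / −0.478 / −0.469 |
| control arm only | 0 | 0.09 / 0.18 / 0.25 | 0.05 / 0.08 / 0.12 |
| control arm only | −0.5 | −0.408 / −0.327 / −0.252 | −0.452 / −0.413 / −0.378 |

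In the control-only rows the experimental arm also loses people (about 7 / 16 / 26–27%), but at random. The week-4 column applies to the repeated-measures form only. The week-12 column applies to that form and to a single-factor ANOVA of the week-12 change.

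Check on the pattern: the slope of the week-12 change on the week-4 change is (1 − ρ) / [2(1 − ρ)] = 0.5, so the week-12 bias should be half the week-4 bias, as the table shows. If the dependence ran in opposite directions in the two arms, the no-effect bias would roughly double (0.18 and 0.35 at week 4, 0.09 and 0.18 at week 12, for 10% and 20% loss).

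**4. An extreme case on raw means.** Suppose exactly the worst-scoring fraction d of one arm at week 4 leaves, nobody leaves the other arm, there is no true effect, and the correlation is 0.6. The shift in the week-4 mean is φ(z_d)/(1 − d).

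- Week 4, raw: 0.195 SD at d = 0.10; 0.350 SD at d = 0.20.
- Week 12, raw: × 0.6 = 0.117 and 0.210 SD.
- Week 4, change: × (1 − 0.6) = 0.078 and 0.140 SD. The SE of a change difference is 0.198 × √(2 × 0.4) = 0.177 SD.
- Week 12, change: × (correlation of weeks 4 and 12 minus correlation of pre-test and week 4). This is zero at equal correlations and 0.350 × (0.7 − 0.5) = 0.07 SD at 0.7 versus 0.5.

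**5. Stacked rows.** With equal correlation ρ, the variance of a person's three-visit mean is (1 + 2ρ)/3, but the model takes 1/3. At ρ = 0.5 the SE of the overall group effect is too small by √2 = 1.41. A change has variance 2(1 − ρ), but the model takes 2, so its SE is too large by 1/√(1 − 0.5) = 1.41.

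**6. Using the data on those who left.** In the setting of step 3, predicting week 12 within each arm from pre-test and week 4 (a stand-in for a likelihood analysis) gave week-12 differences of −0.498 to −0.504 against a true −0.5, and within 0.005 of zero under no effect. In the setting of step 4, simulated with 51 per arm, a likelihood analysis of all observed visits was within 0.01 SD of zero at both visits.

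**The case against.** A reader might infer that the protocol prescribes a completers-only analysis and that the arm comparison is therefore biased. The document supports neither step. Item 6 never says repeated measures and never says complete cases. The single-factor form, which it names first, keeps every week-4 value, so the loss of collected week-4 data does not occur there. Nor does bias follow from withdrawal alone: it is absent when loss is unrelated to response, absent under no effect when the same rule acts in both arms, and material mainly when the dependence differs by arm.

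A reader might also take 0.35 SD as the size of the problem. That figure comes from a deterministic loss of the worst scorers in one arm, on raw week-4 means. A group-by-time interaction tests differences in change, where the same case gives 0.14 SD at week 4, less than one standard error, and about zero at week 12 with equal correlations.

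Finally, rules for missing data and analysis sets commonly sit in the SAP, which is not at hand, so their absence from the protocol is no fault. All of this stands.

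It does not remove the point. Item 6 does choose a family of methods, and none of the three forms makes valid use of all the data held on people who leave. That is a weakness of the stated method, not a gap waiting for a missing-data rule.

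**Conclusion.** The point holds conditionally. Item 6 leaves the model open, and each plausible choice has a weakness once visits are missing: week-4 results are discarded, or week-12 results rest on stayers alone, or correlated measurements are treated as independent.

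With response-dependent withdrawal in one arm only and an assumed 10–20% loss, completers-only bias is roughly 0.1–0.2 SD at week 4 (repeated-measures form) and 0.05–0.1 SD at week 12. Against an SE of 0.198 SD that is about half to one standard error at week 4 and a quarter to a half at week 12. A 0.5 SD benefit under the same withdrawal rule in both arms would be only modestly attenuated.

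Every input except 51 per arm is assumed, so these figures show what could happen, not what the trial should expect. The change is still worth making, because the better method is cheap and also settles which analysis is meant.

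**What to change.** In item 6, for outcomes measured at both post-tests, name a likelihood-based linear mixed model for repeated measures (SPSS MIXED: group, visit, group by visit, unstructured covariance). Include all randomised participants in the arm assigned, with every visit observed, and report the group difference at week 4 and at week 12 from that one model. Keep the ANOVA as a secondary check and state which form it takes.

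The cost is a sentence or two in item 6 and a different procedure in the software already named; no extra participants, visits or measurements are needed. The small downside is that the model relies on missingness depending only on observed data. That is a weaker assumption than a completers-only ANOVA makes, but it cannot be verified from the trial's own data.
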